### **6.2.7 Pharmacokinetic Interactions**

Dovitinib is metabolized mainly by CYP1A1/2 and FMO. FMO is not readily induced or inhibited by any other agents, therefore the drug-drug interactions between dovitinib and FMO inducers/inhibitors are of lesser concern. To a lesser extent, dovitinib could be metabolized by CYP3A4, CYP2C8, and CYP2D6 enzymes.

Though no drug interactions have been studied clinically, drugs that inhibit (ciprofloxacin, clinafloxacin, enoxacin, fluvoxamine, oltipraz, propranolol, rofecoxib, thiabendazole, and zafirlukast) or induce CYP1A1/2 (omeprazole and tobacco) may interact with dovitinib and should be used with caution.

In vitro, dovitinib has a potential to induce CYP1A2 activity 2- to 14-fold, as well as CYP2C9 and CYP2C19 activity to a lesser extent (< 3- to 4-fold). Therefore, CYP1A2, CYP2C9, and CYP2C19 substrates as listed below should also be used with caution:

- **CYP1A2 substrates:** clozapine, cyclobenzaprine, imipramine, mexiletine, naproxen, riluzole, tacrine, and theophylline.
- **CYP2C9 substrates:** losartan, irbesartan, diclofenac, ibuprofen, piroxicam, tolbutamide, glipizide, celecoxib, fluvastatin, naproxen, phenytoin, rosiglitazone, sulfamethoxazole, tamoxifen, tolbutamide, torsemide, and warfarin.
- **CYP2C19 substrates:** diazepam, phenytoin, phenobarbital, lansoprazole, omeprazole, pantoprazole, rabeprazole, amitriptyline, clomipramine, clopidogrel, cyclophosphamide and progesterone.

## 7 Visit schedule and assessments

### 7.1 Study Flow and Visit Schedule

[Table 7-1](#) lists all of the assessments except for laboratory assessments and indicates with an “X” the visits when they are performed. [Table 7-2](#) lists all laboratory assessments. All data obtained from these assessments must be supported in the patient’s source documentation. The table indicates which data are entered into the database (D) or may remain in source documents only (S) (column category). Assessments that generate data for the EDC system are listed.

Since dovitinib is given in a 5 days on/2 days off dosing schedule, day 12 assessments are intended to be performed on the last dosing day of the 2nd week in cycle 1 and cycle 2 and day 26 assessments are intended to be performed on the last dosing day of the 4th week in cycle 1 and cycle 2.

All assessments have a ±3 days window unless otherwise indicated. In the event of public holidays (e.g. Christmas, New Year’s Day), there is a ±5 days window on all assessments. Every effort must be made to follow the schedule of assessments within the windows outlined in the protocol. Additional assessment may be performed as clinically indicated.

**Table 7-1 Visit evaluation schedule**

	Category	Reference to assessment types	Baseline	Cycle 1		Cycle 2		Subsequent cycles	End of study treatment
Visit no.			1	2	3	4	5	6	7+
Day of cycle			-28 to -1	1	12	26	12	26	26 (or 28)
Patient Assessments									
Obtain Informed Consent	D		X						
Demography	D	7.10.1	X						
Inclusion / exclusion criteria	S	5.1, 5.2	X						
Relevant medical history/previous medical conditions	D		X						
Prior/concomitant medications	D		X	Continuous					
Adverse events	D		X	Continuous					
Registration	D		X						
Diagnosis and extent of cancer	D	7.10.2	X						
Prior antineoplastic therapy	D	7.10.3	X						
Vital signs	D	7.10.4	X(<14)	X	X	X	X	X	X
Physical examination	D		X(<14)		X		X	X	X
ECOG PS	D	7.10.5	X(<14)		X		X	X	X
Study Treatment									
Dovitinib dosing a	D			X	X	X	X	X	
Tumor Assessments									
FGFR3 mutation / overexpression status	D	7.10.6	X f						
Cystoscopy	D	7.10.7	X b					X b	
TURBT	D	7.10.7	X c					X c	
Urine cytology	D	7.10.7	X d					X d	
Radiographic Assessments									
CT Abdomen/pelvis	D	7.10.8	X						
Chest x-ray or CT	D	7.10.8	X						

	Category	Reference to assessment types	Baseline	Cycle 1			Cycle 2		Subsequent cycles	End of study treatment
				1	2	3	4	5		
Visit no.			1						7+	
Day of cycle			-28 to -1	1	12	26	12	26	26 (or 28)	
Cardiac Assessments										
2-D Echo or MUGA	D	7.10.9	X						X e	X
ECG	D	7.10.9	X		X	X			X e	X
Correlative Studies										
FGFR1 and FGFR2 mutation status	S	7.10.6		X g						
VEGFR1/2/3 mutation / overexpression status	S	7.10.6		X g						
Plasma FGFR3 mutations	S	7.10.10		X g						
Urine FGFR3 mutations	S	7.10.10		X g						
Tumor dovitinib PK	S	7.10.10							X h	
FGFR & VEGFR Pathway Signaling on TURBT samples	S	7.10.6.6		X i					X i	

- Dovitinib will be dosed on a flat scale of 500 mg (i.e. 5 x 100 mg per capsule/tablet) on a 5 days on/2 days off dosing schedule. See section 6.1.1 for further detail.
- Initial baseline cystoscopy must be performed within 42 days of study registration. Subsequent cystoscopic evaluations will be performed every 3 months +/- 7 days (e.g. 3 month, 6 month, 9 month, 12 month) during the first year of follow-up and as clinically indicated per treating physician thereafter. Note: Patients with residual non-invasive UC tumors with no CIS at initial 3-month cystoscopy/TURBT are not considered relapses. Patients with any component of CIS at initial 3-month cystoscopy and TURBT will be considered relapses and will not continue on dovitinib therapy. Any non-invasive UC tumors (i.e. Ta, T1, Tis) at the 6-month or any subsequent cystoscopy/TURBT is considered relapsed disease. Similarly progression to invasive UC tumors (T2-T4) at any time point is also considered relapsed disease and patients will not continue on dovitinib therapy. See section 7.10.11.2 for details.
- Initial TURBT must be performed within 42 days of study registration. Subsequent TURBT's will be performed every 3 months +/- 7 days (e.g. 3 month, 6 month) during the first 6-months of follow-up and as clinically indicated per treating physician thereafter. Note: Patients with residual non-invasive UC tumors with no CIS at initial 3-month cystoscopy/TURBT are not considered relapses. Patients with any component of CIS at initial 3-month cystoscopy and TURBT will be considered relapses and will not continue on dovitinib therapy. Any non-invasive UC tumors (i.e. Ta, T1, Tis) at the 6-month or any subsequent cystoscopy/TURBT is considered relapsed disease. Similarly progression to invasive UC tumors (T2-T4) at any time point is also considered relapsed disease and patients will not continue on dovitinib therapy. See section 7.10.11.2 for details.
- Initial urine cytology must be performed within 42 days of study registration. Subsequent urine cytologies will be performed every 3 months +/- 7 days (e.g. 3 month, 6 month, 9 month, 12 month) during the first year of follow-up and as clinically indicated per treating physician thereafter
- Subsequent on-treatment Echo and ECG testing to be performed only as clinically indicated
- Mandatory submission of unstained slides from TURBT specimen must be submitted for FGFR3 mutation/overexpression status prior to study registration. Refer to SPM for collection and shipping

guidelines.

- g. Archived pre-treatment tissue samples for study correlates will be collected from enrolled eligible patients. Blood and urine samples for study correlates will be collected at Cycle 1 Day 1 from enrolled eligible patients. The correlative analyses will be completed in batch groupings at study completion. Refer to SPM for collection, processing and shipping guidelines.
- h. Tissue for dovitinib PK analysis will be collected at the initial post-treatment cystoscopy with TURBT performed 3 months +/- 7 days after starting dovitinib therapy. Refer to SPM for collection, processing and shipping guidelines.
- i. Unstained slides are to be submitted from the pre-treatment TURBT specimen and from the post-treatment cystoscopy with TURBT performed 3 months +/- 7 days after starting dovitinib therapy. Refer to SPM for collection and shipping guidelines.

**Table 7-2 Laboratory assessment schedule**

	Test name	Category	Reference to assessment types	Baseline	Cycle 1		Cycle 2		Subsequent cycles	End of study treatment
Visit no.				1	2	3	4	5	6	7+
Day of cycle				-14 to -1	1	12	26	12	26	26
Hematology	Hemoglobin	D	7.10.11	X	X	X	X	X	X	X
	RBC	D	7.10.11	X	X	X	X	X	X	X
	WBC	D	7.10.11	X	X	X	X	X	X	X
	Platelets	D	7.10.11	X	X	X	X	X	X	X
	Differentials:		7.10.11	X	X	X	X	X	X	X
	ANC	D								
	lymphocytes	S								
	monocyte	S								
	eosinophil	S								
	basophil	S								
Chemistry	Urea/BUN	S	7.10.11	X	X	X	X	X	X	X
	Creatinine	D	7.10.11	X	X	X	X	X	X	X
	Total bilirubin	D	7.10.11	X	X	X	X	X	X	X
	ALT	D	7.10.11	X	X	X	X	X	X	X
	AST	D	7.10.11	X	X	X	X	X	X	X
	GGT	D	7.10.11	X	X	X	X	X	X	X
	Alkaline phosphatase	S	7.10.11	X	X	X	X	X	X	X
	Albumin	D	7.10.11	X	X	X	X	X	X	X
	Total protein	S	7.10.11	X	X	X	X	X	X	X
	Calcium	D	7.10.11	X	X	X	X	X	X	X
	Sodium	S	7.10.11	X	X	X	X	X	X	X
	Magnesium	D	7.10.11	X	X	X	X	X	X	X
	Potassium	D	7.10.11	X	X	X	X	X	X	X
	Phosphorous	D	7.10.11	X	X	X	X	X	X	X
	Glucose	S	7.10.11	X	X	X	X	X	X	X
	LDH	D	7.10.11	X	X	X	X	X	X	X
	Amylase	D	7.10.11	X	X	X	X	X	X	X
	Lipase	D	7.10.11	X	X	X	X	X	X	X
Serum lipid profile	Total cholesterol, triglycerides, LDL, HDL	S	7.10.11	X			X		X	X
Coagulation	PT or INR	S	7.10.11	X				X	X a	
	PTT	S	7.10.11	X				X	X a	
	Fibrinogen	S	7.10.11	X				X	X a	

Urinalysis	Dipstick: specific gravity, PH, protein, blood, glucose...	S	7.10.11	X f			X b		X b	X b	
	Microscopic: WBC, RBC, bacteria, casts...	S	7.10.11	X			X b		X b	X b	
Thyroid function	TSH, T3, T4	D	7.10.11	X					X c		X
Cardiac enzymes	CPK, CK-MB, troponin T or I	S	7.10.11	X			X d		X d	X d	
Pregnancy e test		S	7.10.11	X			X		X	X	

aAdditional PT/INR, PTT, and Fibrinogen studies will be performed only as clinically indicated in subsequent treatment cycles.

bAdditional urine dipstick and microscopic studies will be performed only as clinically indicated in subsequent treatment cycles.

cAdditional TSH, T3, and T4 studies will be performed (+/- 5 days) on cycle 3 day 26, cycle 6 day 26 and as clinically indicated in subsequent treatment cycles.

dAdditional CPK, CK-MB, troponin T or I studies will be performed only as clinically indicated in subsequent treatment cycles.

eA serum pregnancy test will be assessed in female patients of childbearing potential within 14 days of registration and on day 26 ( $\pm$  5 days) of all subsequent treatment cycles.

fIf documentation of +1 (+2 for patients with renal cell carcinoma) results for protein on dipstick reading, a 24 hour urine for protein must be obtained

## **7.2 Biomarkers**

All patients will be required to have bladder tumor FGFR3 mutation and over-expression status determined from a TURBT sample obtained within 42 days of registration. All other biomarker analyses will be exploratory in nature and do not need to be performed as part of study screening or eligibility assessments.

## **7.3 Eligibility Screening and Patient Registration**

Patient eligibility will be confirmed through the Hoosier Cancer Research Network's secure web-based electronic data capture system. Once eligibility criteria are entered and the patient is confirmed as eligible, the EDC system will assign a unique patient identification number to the patient, and register the patient.

Patients must be registered prior to starting protocol therapy and begin therapy within 5 working days of registration.

### **Blinding**

The study treatment is not blinded to the patient or the investigator.

## **7.4 Information Collected on Screen Failures**

Patients who sign an informed consent but fail to be started on treatment for any reason will be considered a screen failure. The reason for not being started on treatment and eligibility information will be entered in the EDC system.

## **7.5 Patient Demographics and Other Baseline Characteristics**

At screening/baseline, the following demographic and screening/baseline characteristic data will be collected from all patients:

- Date of birth
- Sex
- Ethnicity
- Race
- Height
- Weight
- Systolic blood pressure
- Diastolic blood pressure
- ECOG performance status
- Cystectomy eligibility status (if ineligible, record reason)
- White blood cell count
- Absolute neutrophil count

- Hemoglobin
- Platelet count
- Creatinine
- AST
- ALT
- Total bilirubin
- Alkaline phosphatase
- Left ventricular ejection fraction
- Charlson comorbidity index (CCI)

The CCI for each patient is determined by summation of relative point values for each patient co-morbidity condition according to the following system:

Conditions assigned 1 point each:

- Myocardial infarct
- Congestive heart failure
- Peripheral vascular disease
- Dementia
- Cerebrovascular disease (CVA with mild or no residual effects or TIA)
- Chronic lung disease
- Connective tissue disease
- Peptic ulcer
- Mild chronic liver disease (i.e. without evidence of portal hypertension, includes chronic hepatitis)
- Diabetes without end-organ damage (excludes diet-controlled alone)

Conditions assigned 2 points each:

- Hemiplegia
- Moderate or severe kidney disease (GFR  $\leq$  60 ml/min by Cockcroft-Gault formula)
- Diabetes with end organ damage (i.e. retinopathy, neuropathy, nephropathy)
- Any cancer (exclude if > 5 years from diagnosis with no active disease)
- Leukemia (acute or chronic)
- Lymphoma

Conditions assigned 3 points each:

- Moderate or severe liver disease (i.e. with evidence of portal hypertension)

Conditions assigned 6 points each:

- Metastatic solid organ cancer
- AIDS

For example, a patient with BCG-refractory urothelial carcinoma (2 pts), type 2 diabetes without end organ damage (1 pt), past history of a non-ST-elevation myocardial infarction (1 pt), with history of chronic obstructive pulmonary disease (1 pt) would have a CCI = 5.

- Bladder tumor stage (Ta, Tis, T1, Ta + Tis, T1 + Tis)
- Number of prior intravesical BCG courses (i.e. BCG x 2 courses → mitomycin C x 1 course → gemcitabine x 1 course = 2 prior BCG courses)
- Number of prior intravesical courses of any type (i.e. BCG x 2 courses → mitomycin C x 1 course → gemcitabine x 1 course = 4 prior intravesical courses)
- Number of prior intravesical agents received (i.e. BCG x 2 courses → mitomycin C x 1 course → gemcitabine = 3 prior agents)
- Date of last intravesical therapy of any kind
- Date of last intravesical BCG therapy
- Tumor FGFR3 mutation status
- Tumor FGFR3 over-expression status

## 7.6 Treatment Period

All patients will be treated until either: 1) relapsed disease is noted; 2) Treatment related toxicity requiring a third dose reduction is encountered; 3) Treatment related toxicity not yet requiring a third dose reduction but per the treating physician's discretion is deemed unsuitable for further dovitinib therapy is encountered; or 4) Patient electively foregoes further dovitinib therapy at any time.

## 7.7 End of Treatment and Premature Withdrawal Visit

Patients who discontinue study drug before completing the study should be scheduled for a visit as soon as possible, at which time all of the assessments listed for the final visit will be performed. The date and reason for stopping the study treatment will be recorded in the eCRF. At a minimum, all patients who discontinue study treatment, including those who refuse to return for a final visit, will be contacted for safety evaluations during the 30 days or 5 half-lives (whichever is longer) following the last dose of study drug.

Patients who discontinue study treatment also should return for tumor assessments per the study calendar and should not be considered withdrawn from the study. If patients refuse to return for these visits or are unable to do so, every effort should be made to contact them or a knowledgeable informant by telephone to determine the date and tumor response status as well as

the date and tumor relapse status. Record the date and tumor response status as well as date and tumor relapse status in the eCRF.

Patients who discontinue study drug should be considered withdrawn from the study after the final visit assessments are performed or when it is clear that the patient will not return for these assessments.

If a withdrawal occurs, or if the patient fails to return for visits, the investigator must determine the primary reason for a patient's premature withdrawal from the study and record this information in the eCRF.

If a patient discontinues study drug, but continues study assessments, the reason for study completion should be recorded in the eCRF.

End of treatment/Premature withdrawal visit is not considered as the end of the study.

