#### **7.7.2 Follow-up for Toxicities**

Patients whose treatment is interrupted or permanently discontinued due to an adverse event or abnormal laboratory value must be followed at least once a week for 4 weeks, and subsequently at 4-week intervals, until resolution or stabilization of the event, whichever comes first. If a patient requires a dose delay of > 14 days from the intended day of the next scheduled dose, then the patient must be discontinued from the study. However, the patient will continue to be followed for toxicity as previously described. All patients will be followed for adverse events and serious adverse events for 30 days following the last dose of dovitinib.

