### **7.9 Follow up Period**

All patients must have safety evaluations for 30 days or 5 half-lives (whichever is longer) after the last dose of study treatment. All patients will be followed for tumor relapse status until tumor relapse is noted or for 12 months beyond last dose of study treatment in patients who stopped dovitinib prior to disease relapse.

Patients lost to follow up should be recorded as such on the eCRF. For patients who are lost to follow-up, the investigator should show "due diligence" by documenting in the source documents steps taken to contact the patient, e.g., dates of telephone calls, registered letters, etc.

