## **10 Statistical Methods and Data Analysis**

### **10.1 General Considerations**

Statistical analysis of this study will be the responsibility of the Department of Biostatistics at IUSM. Parameter estimates and relevant summary statistics will be reported for both efficacy and safety outcomes. Continuous variables will be summarized by means, medians, minima, maxima and standard deviations. Categorical variables will be summarized by frequencies and percentages. Missing data are expected to be rare. For patients that start therapy but do not make it to the primary endpoint evaluation, their 6-month status will be treated as not achieving CR. Consequently, our estimate of 6-month CR rate will be conservative. For secondary outcomes, missing data, if any, will not be imputed and complete-case analysis will be adopted. Additional exploratory analysis will be conducted when appropriate. Changes from the analysis plan will not require an amendment to the protocol unless it changes a significant feature in the protocol.

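### Section 7.7 both retains and withdraws patients who stop dovitinib, which leaves an avoidable route to missing 6-month response data

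*Combined protocol and SAP*

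**What the plan says.** Section 7.7 gives two instructions for the same patients. Its second paragraph says: "Patients who discontinue study treatment also should return for tumor assessments per the study calendar and should not be considered withdrawn from the study". The next paragraph says: "Patients who discontinue study drug should be considered withdrawn from the study after the final visit assessments are performed", or once it is clear that the patient will not come back for those assessments. The section's opening ties the final visit to one arranged as soon as possible after the drug is stopped, "at which time all of the assessments listed for the final visit will be performed". Its last line points the other way: "End of treatment/Premature withdrawal visit is not considered as the end of the study".

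For a dose delay of more than 14 days, section 7.7.2 says "then the patient must be discontinued from the study" and then mentions only toxicity follow-up. Footnote c to the table in 6.1.4 uses the same phrase.

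Section 7.9 says: "All patients will be followed for tumor relapse status until tumor relapse is noted", or for 12 months after the last dose in patients who stopped before relapse. Section 7.8 replaces patients who are prematurely withdrawn within the first 3 months and before the first post-therapy cystoscopy, cytology and TURBT. Section 10.1 says of patients who start therapy but do not reach the primary evaluation that "their 6-month status will be treated as not achieving CR". For secondary outcomes it uses complete cases without imputation.

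**The concern.** The 6-month complete response needs a cystoscopy with TURBT and a urine cytology at 6 months after the start of therapy (3.1.1, 7.10.12.1). Staying on drug is not a condition. A patient who stops at month 4 for toxicity or by choice, both allowed under 7.6, can therefore still be a responder if examined at month 6. If the site treats that patient as withdrawn at the end-of-treatment visit, the examination may not take place and 10.1 fixes the result as non-CR. The same patient may also drop out of the complete-case 1-year relapse-free survival rate. The direction of that error is not known in advance.

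The word withdrawn also triggers replacement in 7.8, so the ambiguity affects who is replaced as well as who is assessed. With 20 patients, small differences in how sites handle these cases can matter.

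**Working it through.** **1. Can the two sentences in 7.7 be reconciled?** One could take the final visit to mean the last scheduled tumor assessment, so that withdrawal comes only after follow-up is complete or refused. The opening paragraph of 7.7 works against this, since it places the final-visit assessments at a visit soon after the drug is stopped. Read as written, the section retains the patient and then withdraws the patient.

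**2. Where does the rest of the text point?**

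| Towards continued assessment | Towards withdrawal |
|---|---|
| 7.10.7.1 and 7.10.7.2: all patients have cystoscopy and cytology every 3 months in year one, and TURBT/biopsy at 3 and 6 months, with no restriction to patients on drug | 7.7, third paragraph |
| 7.9: relapse status followed to relapse or 12 months after last dose | 7.7.2: dose delay over 14 days |
| 4.2: study ends on the same basis | 6.1.4, footnote c: dose interruption over 14 days |
| 7.7, last line | |
| Glossary: stopping drug may or may not coincide with premature withdrawal | |

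The balance favors continued assessment. Section 7.9 does not settle the matter alone, because it requires relapse status and not the 6-month TURBT and cytology.

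**3. Who is affected?** For the primary endpoint, only patients who stop before month 6 without relapse. Those withdrawn before the first post-therapy TURBT are replaced (7.8) and fall outside the Efficacy Set (10.2.5). That leaves mainly stops between about months 3 and 6. This assumes that replaced patients leave the primary denominator, which 10.1 does not state.

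**4. How many responses are needed?** Inputs from 10.8: n = 20, one-sided 90% Agresti-Coull lower bound, expected rate 25%, rate to exclude 10%. With z = 1.2816, z² = 1.6424 and ñ = 20 + 1.6424 = 21.6424:

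p̃ = (x + z²/2)/ñ; lower bound = p̃ − z·√(p̃(1 − p̃)/ñ)

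- x = 3: p̃ = 3.8212/21.6424 = 0.1766; bound = 0.1766 − 0.1050 = 0.0715
- x = 4: p̃ = 4.8212/21.6424 = 0.2228; bound = 0.2228 − 0.1146 = 0.108

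Four responses are needed, so one patient can change the conclusion.

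**5. The plan's own power figure.** P(X ≥ 4) for Binomial(20, 0.25) = 1 − (0.0032 + 0.0211 + 0.0669 + 0.1339) = 0.775. The plan states 0.80. The gap is a separate matter, and nothing here depends on it.

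**6. Illustration of the loss.** The documents give no early-stop rate; 10.1 says only that missing data should be rare. Suppose m of the 20 stop without relapse after the first TURBT, would have responded at 25% if examined, and are all scored non-CR. Power is then P(X ≥ 4) for Binomial(20 − m, 0.25), and the expected observed rate is 25% × (20 − m)/20.

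| m | Expected CR rate | Chance of ≥ 4 responses |
|---|---|---|
| 0 | 25.0% | 0.775 |
| 1 | 23.75% | 0.737 |
| 2 | 22.5% | 0.694 |
| 4 | 20.0% | 0.595 |

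**The case against.** The strongest reply is that the plan already answers the question. Sections 7.10.7.1 and 7.10.7.2 schedule the examinations for all patients, 4.2 and 7.9 continue follow-up after drug is stopped, and the glossary separates stopping drug from leaving the study. On that view, one stray sentence and a loose phrase about dose delays stand against a consistent scheme. The non-CR rule in 10.1 also turns on missing the evaluation, not on being labelled withdrawn, and the plan openly calls the resulting estimate conservative.

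Much of this stands. A reader might infer that the two readings are evenly supported, so that response status simply depends on which sentence a site picks. The documents do not support that, because most of the text favors continued assessment. A reader might also infer a large loss by supposing that 10% to 30% of all patients stop before month 6 and are all scored non-CR. No such rate appears in the documents, and the calculation ignores replacement of withdrawals before the first TURBT.

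The contradiction itself remains. A site can cite 7.7 or 7.7.2 for ending assessments at the end-of-treatment visit. A conservative rule for unavoidable loss is no reason to lose patients who would have attended.

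**Conclusion.** The inconsistency is real and should be fixed. It is a conflict of wording, not a design choice, and the weight of the text limits its likely effect. The exposure is confined mainly to patients who stop without relapse between about months 3 and 6 at sites that act on the withdrawal wording. In the illustration, one such patient costs about 4 points of power (0.775 to 0.737) and four cost 18 points (0.775 to 0.595). These figures assume that the affected patients would have responded at 25%, that every one of them goes unexamined, and that none is replaced. The number affected is unknown. The possible loss from 1-year relapse-free survival cannot be sized from the documents.

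**What to change.** - Reconcile 6.1.4 (footnote c), 7.7, 7.7.2, 7.8 and 7.9 so that discontinuing study treatment and withdrawing from the study are distinct terms, used consistently.
- Remove or reword the sentence in 7.7 that treats patients off drug as withdrawn. State that patients off drug without relapse keep the tumor assessments already scheduled in 7.10.7.1 and 7.10.7.2 unless they withdraw consent.
- Align the replacement trigger in 7.8 with that distinction. Otherwise a patient who stops drug early but stays on study would no longer clearly meet it, since it now depends on withdrawal.

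The criteria for interrupting or stopping dovitinib are outside this point and need no change for it. The cost is a wording amendment. It adds no procedure beyond those in 7.10.7.1 and 7.10.7.2, which the plan describes as standard of care.
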